**Novo Nordisk**

- Date and time of hypoglycaemic episode
- The plasma glucose level before treating the episode (if available)
- Whether the episode was symptomatic
- Whether the subject was able to treat him/herself
- Date and time of last trial product administration prior to episode
- Type and dose of last trial product administration prior to episode
- Date and time of last main meal prior to episode
- Whether the episode occurred in relation to physical activity
- Any sign of fever or other disease
- Whether the subject was asleep when the episode occurred
  - If yes, whether the symptoms of the episode woke up the subject

The answer to the question: "Was subject able to treat him/herself?" must be answered "No" for an episode requiring assistance of another person to actively administer carbohydrate, glucagon, or take other corrective actions. Plasma glucose concentrations may not be available during an event, but neurological recovery following the return of plasma glucose to normal is considered sufficient evidence that the event was induced by a low plasma glucose concentration.

Oral carbohydrates should not be given if the subject is unconscious.

If the question "Was subject able to treat him/herself?" is answered "No", the following information should be recorded:

- Who assisted in the treatment of the hypoglycaemic episode (i.e. family/friend/co-worker or similar, paramedic, doctor or other, please specify)
- Where the treatment was administered (i.e. at home/at friends/at work or similar, in an ambulance, emergency room/hospital or other, please specify)
- Type of treatment provided by other person (i.e. oral carbohydrates, glucagon, IV glucose or other, please specify)
- Were symptoms alleviated after administration of treatment?
- Factors contributing to the episode (i.e. physical activity, missed meal, diet changed, medication error (i.e. overdose, mix-up between products), miscalculation of insulin dose, other factors not listed, please specify or none)
- Did the subject experience seizure?
- Was the subject unconscious/comatose?
- Did the subject experience any of the following symptoms?
  - Autonomic: sweating, trembling, hunger or palpitations
  - Neuroglycopenic: confusion, drowsiness, speech difficulty, visual disturbances, odd behaviour, impaired balance or incoordination
  - General malaise: headache or malaise
- Did the subject experience other symptoms? Please specify

Protocol: Liraglutide  
Trial ID: NN8022-4179  
UTN: U1111-1162-7884  
EudraCT no.: 2014-004415-37

CONFIDENTIAL

Date: 16 July 2020  
Version: 5.0  
Status: Final  
Page: 53 of 125

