#### 3.1 Background information

##### Prader Willi syndrome

Prader-Willi syndrome (PWS) is a genetic disorder characterised by hypotonia with poor sucking reflex, feeding difficulties, and poor weight gain during infancy, hypogonadism, growth hormone insufficiency causing short stature, mild to moderate mental retardation, early childhood-onset hyperphagia and obesity. Birth incidence has been estimated at around 1: 30,000 and population prevalence at about 1: 50,000^6.

Obesity typically manifests in early childhood and is a major cause of morbidity and mortality and is strongly associated with multiple comorbid conditions, including cardiopulmonary compromise, type 2 diabetes mellitus (T2DM), hypertension, thrombophlebitis, chronic leg oedema, and sleep apnoea. Food-seeking behaviour is common in patients with PWS. Left unchecked and untreated, lack of appetite control can lead to morbid obesity, typically manifesting in early childhood. Therefore improvement in weight control remains the most important goal of any PWS treatment programme.

A study by Brambilla et al. investigated metabolic syndrome in 109 children with PWS aged 2–18 years (50 with obesity and 59 without obesity) and 96 controls with obesity without PWS. 16% of the subjects with obesity and PWS had metabolic syndrome (very close to that observed in the controls with obesity), whereas none of the subjects with PWS without obesity had metabolic syndrome, suggesting that obesity status play a key role in the development of metabolic syndrome.

For treatment and prevention of obesity in PWS, low calorie and well-balanced diets with rigorous supervision and restriction of food access combined with regularly scheduled meals and physical activities are recommended. The treatment of obesity in PWS is difficult and requires a comprehensive multidisciplinary approach with establishment of rigid structures to limit food intake and promote supervised physical activity. Bariatric surgery is not recommended for children with PWS.

The role of pharmacotherapy in PWS is uncertain. No medication has shown long-term effectiveness in controlling appetite. In one study, adult patients with PWS were found to have elevated ghrelin concentrations compared to the reference population, raising the possibility that

Protocol: Liraglutide  
Trial ID: NN8022-4179  
UTN: U1111-1162-7884  

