#### 4.2.2.3 Supportive secondary safety endpoints

- Number of treatment-emergent adverse events during the trial
- Number of severe treatment emergent episodes of hypoglycaemia
- Number of blood glucose confirmed symptomatic episodes of hypoglycaemia
- Occurrence of anti-liraglutide antibodies

Change from baseline to 16 and 52 weeks in:

- Electrocardiogram (ECG)
- Pulse
- Laboratory parameters:
  - Haematology: haemoglobin, haematocrit, thrombocytes, erythrocytes, leukocytes, differential count (eosinophils, neutrophils, basophils, lymphocytes, monocytes)
  - Biochemistry: creatinine, creatine kinase (CPK), urea, albumin, bilirubin (total), alanine aminotransferase (ALT), aspartate aminotransferase (AST), alkaline phosphatase, sodium, potassium, calcium total, calcium albumin corrected, amylase, lipase, and carcinoembryonic antigen (CEA)
  - Hormone levels including: calcitonin, insulin-like growth factor-1 (IGF-1), thyroid stimulating hormone (TSH), free thyroxine (free T4), prolactin, adrenocorticotrophic

Protocol: Liraglutide  
Trial ID: NN8022-4179  
UTN: U1111-1162-7884  
EudraCT no.: 2014-004415-37

~~CONFIDENTIAL~~

Date:	16 July 2020	Novo Nordisk
Version:	5.0	
Status:	Final	
Page:	27 of 125	

hormone (ACTH), cortisol, dehydroepiandrosterone sulfate (DHEAS), luteinising hormone (LH), follicle stimulating hormone (FSH), estradiol (females), testosterone (males)

- Pubertal status
- Physical examination including height
- Part A only: Mental health assessed by Columbia Suicidality Severity Rating Scale (C-SSRS) and Patient Reported Health Questionnaire-9 (PHQ-9)

\*Key supportive secondary endpoint prospectively selected for posting on clinicaltrials.gov and EudraCT)

Protocol: Liraglutide  
 Trial ID: NN8022-4179  
 UTN: U1111-1162-7884  
 EudraCT no.: 2014-004415-37

[figure not shown]
CONFIDENTIAL

Date: 16 July 2020  
 Version: 5.0  
 Status: Final  
 Page: 28 of 125  
 Novo Nordisk

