### Novo Nordisk classification of hypoglycaemia

In normal physiology, symptoms of hypoglycaemia occur below a plasma glucose level of 3.1 mmol/L (56 mg/dL). Therefore, Novo Nordisk has included hypoglycaemia with plasma glucose levels below this cut-off point in the definition of blood glucose (BG) confirmed hypoglycaemia.

Novo Nordisk uses the following classification in addition to the ADA classification:

- Severe hypoglycaemia according to the ADA classification.
- Symptomatic BG confirmed hypoglycaemia: An episode that is BG confirmed by plasma glucose value < 3.1 mmol/L (56 mg/dL) **with** symptoms consistent with hypoglycaemia.
- Asymptomatic BG confirmed hypoglycaemia: An episode that is BG confirmed by plasma glucose value < 3.1 mmol/L (56 mg/dL) **without** symptoms consistent with hypoglycaemia.
- Severe or BG confirmed symptomatic hypoglycaemia: An episode that is severe according to the ADA classification or BG confirmed by a plasma glucose value < 3.1 mmol/L (56 mg/dL) **with** symptoms consistent with hypoglycaemia.
- BG confirmed hypoglycaemia: An episode that is BG confirmed by a plasma glucose value < 3.1 mmol/L (56 mg/dL) **with** or **without** symptoms consistent with hypoglycaemia.
- Severe or BG confirmed hypoglycaemia: An episode that is severe according to the ADA classification or BG confirmed by a plasma glucose value < 3.1 mmol/L (56 mg/dL) with or without symptoms consistent with hypoglycaemia.

Protocol: Liraglutide  
 Trial ID: NN8022-4179  
 UTN: U1111-1162-7884  
 EudraCT no.: 2014-004415-37

[figure not shown]
CONFIDENTIAL

Date: 16 July 2020  
 Version: 5.0  
 Status: Final  
 Page: 99 of 125

Novo Nordisk

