### ADA classification of hypoglycaemia

- Severe hypoglycaemia: An episode requiring assistance of another person to actively administer carbohydrate, glucagon, or take other corrective actions. Plasma glucose concentrations may not be available during an event, but neurological recovery following the return of plasma glucose to normal is considered sufficient evidence that the event was induced by a low plasma glucose concentration.
- Asymptomatic hypoglycaemia: An episode not accompanied by typical symptoms of hypoglycaemia, but with a measured plasma glucose concentration  $\leq 3.9$  mmol/L (70 mg/dL).
- Documented symptomatic hypoglycaemia: An episode during which typical symptoms of hypoglycaemia are accompanied by a measured plasma glucose concentration  $\leq 3.9$  mmol/L (70 mg/dL).
- Pseudo-hypoglycaemia: An episode during which the person with diabetes reports any of the typical symptoms of hypoglycaemia with a measured plasma glucose concentration  $> 3.9$  mmol/L (70 mg/dL) but approaching that level.
- Probable symptomatic hypoglycaemia: An episode during which symptoms of hypoglycaemia are not accompanied by a plasma glucose determination but that was presumably caused by a plasma glucose concentration  $\leq 3.9$  mmol/L (70 mg/dL).

Note: Glucose measurements are performed with capillary blood calibrated to plasma equivalent glucose values

Figure 17–1 ADA classification of hypoglycaemia

Protocol: Liraglutide  
Trial ID: NN8022-4179  
UTN: U1111-1162-7884  
EudraCT no.: 2014-004415-37

CONFIDENTIAL

Date: 16 July 2020  
Version: 5.0  
Status: Final  
Page: 100 of 125

Novo Nordisk

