**Table 6-1 New classification of hypoglycaemia**

Level	Glycaemic criteria	Description
Hypoglycaemia alert value (level 1)	< 3.9 mmol/L (70 mg/dL) and $\geq$ 3.0 mmol/L (54 mg/dL)	Sufficiently low for treatment with fast-acting carbohydrate and dose adjustment of glucose-lowering therapy
Clinically significant hypoglycaemia (level 2)	< 3.0 mmol/L (54 mg/dL)	Sufficiently low to indicate serious, clinically important hypoglycaemia
Severe hypoglycaemia (level 3)	No specific glucose threshold	Hypoglycaemia associated with severe cognitive impairment requiring external assistance for recovery
Unclassifiable	Unclassifiable	Episodes which could not be classified according to the above new classifications

Notes: The above terms 'hypoglycaemia alert value' for level 1 and 'clinically significant hypoglycaemia' for level 2 were adapted by Novo Nordisk from IHSG 2017, ADA 2018, ISPAD 2018 recommendations for hypoglycaemia. 'Severe hypoglycaemia' (level 3) term was as defined by ADA 2013 and ISPAD 2018.

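### Severe hypoglycaemia rests on needing another person's help, whatever the reason, so an alert but dependent child's low can count as severe; this does not match the SAP's level 3

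*Protocol*

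**What the plan says.** Three places in the two documents bear on what a severe episode is.

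- **The form.** Protocol 8.5.2 asks whether the subject was able to treat him- or herself. The answer must be No "for an episode requiring assistance of another person to actively administer carbohydrate, glucagon, or take other corrective actions".
- **The protocol classification.** Section 17.4.1.2 gives the American Diabetes Association (ADA) class as "Severe hypoglycaemia: An episode requiring assistance of another person to actively administer carbohydrate", continuing as on the form. No glucose value is needed: "Plasma glucose concentrations may not be available during an event". The sponsor's own classification in the same section takes this over ("Severe hypoglycaemia according to the ADA classification") and uses it in two composites, severe or glucose-confirmed, and severe or glucose-confirmed symptomatic.
- **The SAP classification.** SAP 5.4.1.3 and 6.3.1.5 add a newer three-level scheme. Table 6-1 describes level 3 as "Hypoglycaemia associated with severe cognitive impairment requiring external assistance for recovery". The note under the table says that the severe term follows ADA 2013 and ISPAD 2018.

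The endpoint affected is in Protocol 4.2.2.3: "Number of severe treatment emergent episodes of hypoglycaemia". SAP 5.4.1.3 summarises it descriptively, without a test.

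**The concern.** Needing help is a good marker of impairment in a person who normally treats his or her own lows. This population is different. Part B enrols children from 6 to under 12 years. Protocol 3.1 lists intellectual disability among the features of the syndrome and says that management calls for "rigorous supervision and restriction of food access". Section 17.1 relies on close oversight by family or care staff when it justifies a low withdrawal rate. Such a child may need another person to treat any low, including a mild one without impaired awareness.

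The definition does not ask why help was needed. If some sites answer No for dependence and others only for impairment, the severe count mixes two kinds of event, and a reader of the tables cannot tell them apart. With 57 planned subjects, a few such episodes could make up much of the count. The SAP's second scheme would be the natural place to make the distinction, but it does not say how level 3 is obtained from the form.

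**Working it through.** The plan gives no figure to reproduce, so the check sets the definitions side by side.

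**1. Conditions in each definition**

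| | Another person's help required | Impairment condition | Rule for age or supervision |
|---|---|---|---|
| Form item, Protocol 8.5.2 | yes | none | none |
| ADA severe, Protocol 17.4.1.2 | yes | none | none |
| Level 3, SAP Table 6-1 | yes | severe cognitive impairment | none |

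The form item and the ADA class share their wording. That a No answer yields a severe episode is an inference from this match, since neither document writes the derivation out.

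**2. Illustrative episodes** (constructed for this check, not taken from the documents)

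| Episode | Protocol severe | SAP level 3 as described |
|---|---|---|
| A. Alert, 3.7 mmol/L, able to treat the low, parent hands over juice | no: help given but not required | no; level 1 |
| B. Alert, 3.7 mmol/L, unable to treat it alone because food is locked away or the child is too young or disabled | can be yes: help required | no; level 1 |
| C. Confused, 2.5 mmol/L, carer gives glucose | yes | only if confusion is taken as severe impairment; otherwise level 2 |
| D. Unconscious, no glucose value, carer gives glucagon, recovers | yes | yes |

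Episode B is the problem. Its 3.7 mmol/L lies above the sponsor's confirmation cut-off of 3.1 mmol/L, so it enters both composites only through the word severe. Episode C shows that level 3 cannot be programmed as it stands, because the table does not say which recorded sign amounts to severe cognitive impairment.

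**3. The note to Table 6-1.** It ties level 3 to ADA 2013. The ADA severe class, as the protocol reproduces it, has no cognitive condition. The description and the note therefore lead to different counts for episode B.

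**4. Data available.** For every No answer, 8.5.2 also collects seizure, unconsciousness or coma, a list of neuroglycopenic symptoms, who helped, and the type of treatment. Episodes B, C and D can be told apart from existing fields.

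**5. Size.** The number of affected episodes is (No episodes) × (share of them without impairment signs). The documents give neither factor. All they give is the planned number of younger children, 24 of 57 (24/57 = 0.42).

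**The case against.** The strongest reply has five parts.

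- **The test is whether help was required, not whether it was given.** A reader might infer that every low treated by a parent becomes severe. The text does not support that, as episode A shows. It stands that such episodes can be counted as severe, not that they are.
- **Two parallel schemes are not a contradiction.** A reader might say that the protocol breaks the SAP's own rule. Table 6-1 is an additional summary, so this is too strong. What remains is that two rows labelled severe carry different descriptions and that the table's note points back to the broader one.
- **The data exist.** A reader might infer that impairment is not recorded. It is, through several fields, for every No answer. The gap is the derivation rule.
- **The consequences are limited.** The endpoint is supportive and untested, the same rule applies in both arms, and the first 16 weeks are blinded. The SAP reports part A and part B separately, as well as the double-blind and open-label periods. All of this stands. But those splits do not separate the two kinds of event within a severe row. After allocation is revealed at visit 10, carers' readiness to step in could also differ by arm, though that is an inference.
- **Over-counting is the cautious direction, and narrowing a recognised safety definition late is undesirable.** This is persuasive and is why the ADA count should stay. Treating any single symptom, such as drowsiness, as severe impairment would also be open to dispute.

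Some sources are not available here: Figure 17-1 is not shown, the SAP leaves further specifications to its programming document, and the cited paediatric guideline has not been seen. Any of them might contain a coding rule. Neither the protocol nor the SAP states one.

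**Conclusion.** The point holds as a limited one. The severe class depends on required assistance, with no condition separating help needed because of neuroglycopenia from help needed only because of age, intellectual disability or supervised food access. In this population an alert child's low can be counted as severe, and that does not match the SAP's description of level 3.

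The effect is confined to a named supportive safety count and the two composites that include severe episodes. The co-primary endpoints, the error rate and the sample size are untouched. No number of misclassified episodes can be given. Any percentage would rest on guessed shares of carer-treated lows, and the conclusion does not need one.

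The conclusion assumes that a No answer is what makes an episode severe, and that no coding rule sits in material outside the two documents. It is worth acting on because one derived flag from existing fields would let the endpoint show what it cannot show now.

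**What to change.** In the SAP hypoglycaemia tables and section 6.3.1.5, before database lock:

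1. Keep the unmodified ADA severe count as the endpoint.
2. Below it, split the episodes in which the subject could not treat him- or herself into those with and those without a recorded seizure, unconsciousness or coma, or neuroglycopenic symptom.
3. State which of these fields give level 3, and reconcile Table 6-1 and its note with Protocol 8.5.2 and 17.4.1.2.
4. In the new classification only, place the remaining No episodes by glucose value. Those without a usable value go to the existing unclassifiable row.
5. List every No episode individually, with its symptoms, glucose value, helper and treatment.

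The cost is a few sentences of SAP text, one derived flag and one listing, with no new data collection. The drawback is that incomplete symptom entries could place an impaired episode in the lesser group; the retained ADA row and the listing cover that risk.

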**Novo Nordisk**

- Description of the episode, if applicable

A hypoglycaemic episode form must be filled in for each hypoglycaemic episode. If the hypoglycaemic episode fulfils the criteria for an SAE then an AE form and a safety information form (SIF) must also be filled in, see section [12](#).

### **8.5.2.1 Self-measured blood glucose (SMBG)**

At V3, subjects are provided with a blood glucose (BG) meter including BG meter auxiliaries and instructions for use. The subjects or their LAR will be instructed in how to use and calibrate the device, according to the manufacturer's instructions. Instruction will be repeated as necessary during the trial.

The BG meters use test strips calibrated to plasma values. Therefore, all measurements performed with capillary blood are automatically calibrated to plasma equivalent glucose values, which will be shown on the display.

At each visit, the subject or subject's LAR must demonstrate how to use the BG meter device by measuring the subject's blood glucose value, preferably by using the subject's own BG meter. The SMBG value must be documented in the subject's medical record.

During dose escalation the SMBG measurement must be done before instructing the subject in dose escalation (section [8.1.7](#)). In case the value fulfils the criteria of a hypoglycaemic episode this must be recorded in the eCRF (section [8.5.2](#)).

Subjects or their LAR must be instructed to do a SMBG in between visits in case a hypoglycaemic episode is suspected (section [8.5.2](#)). The subjects must be instructed to contact the investigator in case of low SMBGs.

Subjects or their LAR should be instructed in how to record the results of the SMBGs in the diaries. The record of each SMBG should include date, time and value (section [8.7.3.2](#)). All hypoglycaemic episodes from the diary must be transcribed into the eCRF.

### **8.5.3 Pulse**

Pulse (beats per minute) must be recorded after resting for 5 minutes in a sitting position.

Any "abnormal, clinically significant" findings at screening must be recorded as medical history/concomitant illness in the eCRF and in the subject's medical record.

Any clinically significant worsening or new clinically significant findings after V2 must be reported as an AE in accordance with section [12](#).

Protocol: Liraglutide  
Trial ID: NN8022-4179  
UTN: U1111-1162-7884  
EudraCT no.: 2014-004415-37

~~CONFIDENTIAL~~

Date: 16 July 2020  
Version: 5.0  
Status: Final  
Page: 54 of 125

**Novo Nordisk**

#### **8.5.4 Electrocardiogram – 12 lead**

A 12-lead ECG must be performed and interpreted locally by the investigator. ECG print-outs must be evaluated, signed and dated by the investigator.

The evaluation of ECGs must follow the categories:

- Normal
- Abnormal, clinically significant yes/no

ECG performed for any reason unrelated to this trial within 12 weeks prior to V2 is acceptable provided no clinical symptoms suggestive of cardiac disease have been identified or occurred prior to enrolment. If an ECG is performed before the subject has signed the informed consent form, it must be documented in the subject's medical records that the reason for performing the procedure is not related to this trial. It is allowed to perform the screening ECG after V2 but prior to V3.

Any "abnormal, clinically significant" findings at screening must be recorded as medical history/concomitant illness in the eCRF and in the subject's medical record.

ECGs performed within 30 days prior to the subsequent visits where an ECG is scheduled is acceptable (section [2](#)).

Any clinically significant worsening or new clinically significant findings after V2 must be reported as an AE in accordance with section [12](#).

#### **8.5.5 Pregnancy tests**

All females of childbearing potential must have pregnancy tests performed as described below. For documentation of menstrual periods see section [8.7.3.3](#).

